Grade 2 diarrhea	
Guidelines for the management of diarrhea:
 
 
Evaluate patient carefully including laboratory assessments (chemistry, liver function tests and lipase)
 
Loperamide 4 mg at the first onset of diarrhea, then 2 mg every 2 hours around-the-clock until diarrhea free for at least 12 hours. Patients may take loperamide 4 mg every 4 hours during the night. These doses should not be used for more than 48 hours due to the risk of paralytic ileus.
 
For patients that cannot tolerate loperamide or do not get adequate relief with maximum doses, standard doses of LOMOTIL® (diphenoxylate/atropine) may be added or used instead of loperamide.
 
Additional antidiarrheal measures, such as octreotide, may be used at the discretion of the investigator or treating physician
 
 
If the above measures have not worked, or patient has progressed to Grade 2, or after Grade 1 with no
	
Guidelines for the management of diarrhea:
 
 
Evaluate patient carefully including laboratory assessments (chemistry, liver function tests and lipase)
 
Loperamide 4 mg at the first onset of diarrhea, then 2 mg every 2 hours around-the-clock until diarrhea free for at least 12 hours. Patients may take loperamide 4 mg every 4 hours during the night. These doses should not be used for more than 48 hours due to the risk of paralytic ileus.
 
For patients that cannot tolerate loperamide or do not get adequate relief with maximum doses, standard doses of LOMOTIL® (diphenoxylate/atropine) may be added or used instead of loperamide.
 
Additional antidiarrheal measures, such as octreotide, may be used at the discretion of the investigator or treating physician
 
 
If the above measures have not worked, or patient has progressed to Grade 2, or after Grade 1 with no

Confidential

 Document State: Effective (Controlled)  
 CONFIDENTIAL

Dose Modification Criteria for AL101 -Related Adverse Events	AL101 modification	
	Note: for any questions, please contact the Sponsor's Medical Monitor.	
	Cohort 1 (4 mg QW IV)	Cohort 2 (6 mg QW IV)

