	
improvement within 3 days with maximum doses of loperamide:
 
 
• Patient may be treated with dexamethasone at a dose of 8 mg every 8 hours (Q8h) for up to 5 days. If still no improvement in symptoms, the patient may continue with the dexamethasone or consider switching to budesonide 9 mg once daily (QD). Refer to Section 7.1.2 for additional instructions on premedication with steroids.
 
 
Dose modifications for AL101:
 
Interrupt AL101 until resolution to <math>\leq</math> Grade 1 (refer to Section 7.1.2 for management guidelines for diarrhea and above for management guidelines for diarrhea).
 
Decrease AL101 dose to 2.4 mg QW.
 
If the diarrhea does not resolve to Grade 1 by 14 days, the patient will be discontinued from AL101 (refer to Section 4.5 for early withdrawal of patients from therapy or assessment).
 
If treatment interruption is longer than 28 days, the patient will be discontinued from AL101 (refer to Section 4.5 for early withdrawal of patients from therapy or assessment).
	
improvement within 3 days with maximum doses of loperamide:
 
 
• Patient may be treated with dexamethasone at a dose of 8 mg Q8h for up to 5 days. If still no improvement in symptoms, the patient may continue with the dexamethasone or consider switching to budesonide 9 mg QD. Refer to Section 7.1.2 for additional instructions on premedication with steroids.
 
 
Dose modifications for AL101:
 
Interrupt AL101 until resolution to <math>\leq</math> Grade 1 (refer to Section 7.1.2 and above for management guidelines for diarrhea).
 
Change dose regimen to 6 mg 2 weeks on / 1 week off for first episode
 
Decrease AL101 dose to 4 mg QW for second episode and to 2.4 mg QW for third episode.
 
If the diarrhea does not resolve to Grade 1 by 14 days, the patient will be discontinued from AL101 (refer to Section 4.5 for early withdrawal of patients from therapy or assessment).
 
If treatment interruption is longer than 28 days, the patient will be discontinued from AL101 (refer to Section 4.5 for early withdrawal of patients from therapy or assessment).

Grade 3 diarrhea	Guidelines for the management of diarrhea:	Guidelines for the management of diarrhea:

Confidential

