### 1. Treat with loperamide

Loperamide should be started at the earliest sign of (1) a poorly formed or loose stool, (2) the occurrence of 1 to 2 more bowel movements than usual in 1 day, or (3) an increase in stool volume or liquidity. Loperamide may be taken in the following manners: 4 mg at the first onset of diarrhea, then 2 mg every 2 hours around-the-clock until diarrhea free for at least 12 hours. Patients may take loperamide 4 mg every 4 hours during the night. This dosing regimen is higher than the standard dose of loperamide, but is typical for the treatment of diarrhea caused by anticancer therapy ([Real, 2009](#)). These doses should not be used for more than 48 hours due to the risk of paralytic ileus. Patients should be provided with loperamide at the initial treatment visit so that they have sufficient supply on hand in case antidiarrheal support is required. It is important that loperamide is taken as instructed, as some cases of higher-grade diarrhea have occurred in patients not taking the maximum doses, and these cases have improved after loperamide was taken more frequently. For patients who cannot tolerate loperamide or do not get adequate relief with maximum doses, standard doses of LOMOTIL® (diphenoxylate/atropine) may be added or used instead of loperamide. Additional antidiarrheal measures, such as octreotide, may be used at the discretion of the Investigator or treating physician.

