#### 4. Treat with dexamethasone

For Grade 2 or higher diarrhea that is not adequately controlled with loperamide and dose interruption, administration of dexamethasone may be considered at the discretion of the treating physician/investigator. In nonclinical models of other GSIs, coadministration of dexamethasone has been shown to decrease the severity of intestinal pathology. (Real, 2009; Wei, 2010). Dexamethasone may be administered per os (PO) or IV, as appropriate. As there is no reported human experience with the use of dexamethasone for this indication, it is not known whether this effect will occur in humans at achievable exposures of dexamethasone. In a small number of cases, administration of dexamethasone 8 mg to 10 mg daily, followed by tapering over several days, may have contributed to the improvement of diarrhea. If, in the judgment of the investigator, it is in the patient's best interest to receive additional treatment with AL101 (for example, the patient has a response to therapy), dexamethasone co-administration with future doses may be used after discussion with the Sponsor/medical monitor. In such cases, dexamethasone 8 mg to 10 mg daily for 2 days to 3 days, beginning on the day of AL101 dosing followed by tapering over several days, may be appropriate.

For diarrhea associated with signs of colitis (e.g., fever, peritoneal signs, or significant GI bleeding), administration of dexamethasone and antibiotics should be considered. Also, inpatient hospitalization, bowel rest, and radiological evaluation may be appropriate if there are signs of possible intestinal perforation.

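### One of three dexamethasone triggers in the Grade 2 diarrhea row of Table 6 implies 3 days on maximum-dose loperamide, while the same row limits those doses to 48 hours

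*Protocol*

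**What the plan says.** Protocol Section 6.6, Table 6, Grade 2 diarrhea, same content in both cohort columns:

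- The loperamide regimen is "Loperamide 4 mg at the first onset of diarrhea, then 2 mg every 2 hours around-the-clock" until the patient has been free of diarrhea for a set period, with a less frequent night-time option.
- The limit on that regimen is "These doses should not be used for more than 48 hours due to the risk of paralytic ileus".
- If loperamide is not tolerated or gives too little relief, diphenoxylate/atropine "may be added or used instead of loperamide". Octreotide is left to the investigator's discretion.
- The condition for dexamethasone begins "If the above measures have not worked, or patient has progressed to Grade 2, or after Grade 1 with no" and, across a page break, ends "improvement within 3 days with maximum doses of loperamide".
- The step that follows is permissive. In the Cohort 1 column: "Patient may be treated with dexamethasone at a dose of 8 mg every 8 hours (Q8h) for up to 5 days".

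Section 6.6.2, item 1, repeats the regimen and the 48-hour limit and adds: "This dosing regimen is higher than the standard dose of loperamide". Item 4 of that section has its own dexamethasone step with no 3-day condition: "For Grade 2 or higher diarrhea that is not adequately controlled with loperamide and dose interruption, administration of dexamethasone may be considered".

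**The concern.** A time limit and a time-based trigger in one table row do not fit together. A site that follows the 3-day clause to the letter keeps a patient on the listed loperamide regimen for a day longer than the row advises, and the row gives paralytic ileus as the reason for the limit. A site that stops at 48 hours has not met the 3-day condition as worded.

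The protocol leans on these guidelines. Section 1.3.2 credits them with a Grade 3 diarrhea rate of 3.4% in this study against 19.1% in Study CA216001. Sections 1.3.2 and 1.4.1 use control of gastrointestinal toxicity to support 6 mg weekly, although the previous developer had recommended 4 mg as the maximum tolerated weekly dose. Instructions that carry this much weight should not contradict themselves on a named risk.

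**Working it through.** The plan states no figure to reproduce here, so the check is a side-by-side reading with unit arithmetic.

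**1. The two durations.** The limit is 48 h (Table 6; Section 6.6.2, item 1). The trigger period is 3 days × 24 h = 72 h. The difference is 72 − 48 = 24 h and the ratio is 72 / 48 = 1.5.

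**2. Is the 48-hour figure a slip?** It appears in the Grade 1, 2, 3 and 4 rows in both columns (4 × 2 = 8 places) and again in Section 6.6.2. The 3-day clause appears only in the Grade 2 row, once per column.

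**3. What are maximum doses?** The term has no formal definition. Section 6.6.2, item 1, sets out the listed regimen, describes it as above standard, and then uses the term when discussing patients who took less. The protocol gives no other loperamide dose for managing diarrhea. Taking the term to mean the listed regimen is the natural reading, but it remains an assumption.

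**4. What the literal reading implies.** With the regimen taken without a break:
- by 48 h: 4 mg + 24 × 2 mg = 52 mg
- by 72 h: 4 mg + 36 × 2 mg = 76 mg
- ratio: 76 / 52 = 1.46

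The night-time option has the same hourly rate (4 mg per 4 h = 2 mg per 2 h). No passage orders uninterrupted dosing to 72 h, so the 76 mg total only illustrates the literal reading.

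**5. The three triggers, joined by *or*.**

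| Trigger | Minimum time on loperamide |
|---|---|
| The measures listed above it have failed | none stated |
| Progression to Grade 2 | none |
| Grade 1 without improvement on maximum doses | 3 days |

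Only the third conflicts with the limit. The corresponding sentence in the Grade 3 row has no 3-day condition.

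**6. Which text covers a patient who stays at Grade 1?** The Grade 1 row has no steroid step and no time point for escalation. Section 6.6.2, item 4, concerns Grade 2 or higher. The second trigger does not apply. The first sits in the Grade 2 row, and if it covered Grade 1 at any time, the third would be redundant. The third is therefore the only trigger that explicitly addresses persistent Grade 1 diarrhea, and it is the one that conflicts.

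**The case against.** The strongest reply is that a site can work within the text. It can stop maximum-dose loperamide at 48 hours, use diphenoxylate/atropine or octreotide, and treat the first trigger as met. The 3 days can also be read as the point at which improvement is judged, and not as 72 hours of continuous dosing. The steroid step is optional, the 48-hour limit is advice in form, and Section 6.6.2 leaves room for clinical judgment. Section 7.1.2 gives all patients dexamethasone around infusions, and Section 7.1.3 permits dexamethasone for gastrointestinal toxicity in Cohort 2 after consultation with the medical monitor.

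Much of this stands, and it rules out several stronger readings that a reader might infer:

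- *Rescue for Grade 2 diarrhea waits 3 days.* It does not. The 3-day wording is the tail of a sentence split by a page break, and progression to Grade 2 is itself a trigger.
- *Sites cannot comply with both statements.* They can, by the routes above.
- *Nothing is provided between 48 and 72 hours.* The row allows other antidiarrheals.
- *All 87 patients (45 + 42) are exposed, or more than 30% of them.* The first figure is the combined enrolment ceiling. The second comes from a preliminary safety set of 29 patients and counts diarrhea regardless of causality; it says nothing about persistent Grade 1 events.
- *AL101 interruptions and dose changes will vary as a result.* In this row they follow the diarrhea grade, not the start of dexamethasone, so such an effect is not shown.

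What does not stand is that the text is therefore consistent. Judging improvement on day 3 after stopping at 48 hours needs words that the row does not contain. Switching drugs at 48 hours leaves the third condition unmet as worded. The Section 7.1.3 permission is general, applies to Cohort 2 only, and gives no trigger for persistent Grade 1 diarrhea.

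**Conclusion.** The inconsistency is real and narrow. One of three alternative dexamethasone triggers, in both cohort columns, implies 72 hours on a loperamide regimen that the same row and Section 6.6.2 limit to 48 hours: 24 hours, or half as long again. This rests on two readings, that maximum doses means the listed regimen and that the 3 days are days on that regimen. Both are natural; neither is stated outright.

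The affected group is patients whose diarrhea stays at Grade 1 without improving on maximum-dose loperamide. The documents give no count of them, so the size cannot be expressed in patients. The primary endpoint, its analysis and the sample size are untouched. The point merits correction because the conflict concerns a safety limit with a named risk, in guidelines that the protocol uses to support the 6 mg cohort.

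**What to change.** The sponsor's clinical team should reconcile the Grade 2 row of Table 6, in both cohort columns, with the Grade 1 row and with Section 6.6.2, items 1 and 4. The time period in the trigger and the stated limit on loperamide use should agree, and it should be clear which text governs persistent Grade 1 diarrhea. Stating what is meant by maximum doses would remove the remaining ambiguity. Which duration or rule is right is a clinical decision, and no view on it is offered here.

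The cost is one wording correction, carried into the related passages, and a clarification letter to sites ahead of the next amendment. It needs no added procedures and no change to the SAP.

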	
 
Evaluate patient carefully including laboratory assessments (chemistry, liver function tests and lipase)
 
Loperamide 4 mg at the first onset of diarrhea, then 2 mg every 2 hours around-the-clock until diarrhea free for at least 12 hours. Patients may take loperamide 4 mg every 4 hours during the night. These doses should not be used for more than 48 hours due to the risk of paralytic ileus.
 
For patients that cannot tolerate loperamide or do not get adequate relief with maximum doses, standard doses of LOMOTIL® (diphenoxylate/atropine) may be added or used instead of loperamide.
 
Additional antidiarrheal measures, such as octreotide, may be used at the discretion of the investigator or treating physician
 
 
If the above measures have not worked, or patient has progressed to Grade 3:
 
 
Treat with dexamethasone at a dose of 8 mg Q8h for up to 5 days. If still no improvement in symptoms, the patient may continue with the dexamethasone or consider switching to budesonide 9 mg QD. Refer to Section 7.1.2 for additional instructions on premedication with steroids.
 
 
Dose modifications for AL101:
	
 
Evaluate patient carefully including laboratory assessments (chemistry, liver function tests and lipase)
 
Loperamide 4 mg at the first onset of diarrhea, then 2 mg every 2 hours around-the-clock until diarrhea free for at least 12 hours. Patients may take loperamide 4 mg every 4 hours during the night. These doses should not be used for more than 48 hours due to the risk of paralytic ileus.
 
For patients that cannot tolerate loperamide or do not get adequate relief with maximum doses, standard doses of LOMOTIL® (diphenoxylate/atropine) may be added or used instead of loperamide.
 
Additional antidiarrheal measures, such as octreotide, may be used at the discretion of the investigator or treating physician
 
 
If the above measures have not worked, or patient has progressed to Grade 3:
 
 
Treat with dexamethasone at a dose of 8 mg Q8h for up to 5 days. If still no improvement in symptoms, the patient may continue with the dexamethasone or consider switching to budesonide 9 mg QD. Refer to Section 7.1.2 for additional instructions on premedication with steroids.
 
 
Dose modifications for AL101:

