### **7.1.3      Allowed Medications**

All treatments that the Investigator considers necessary for a patient's welfare may be administered at the discretion of the Investigator in keeping with the community standards of medical care. All concomitant medication will be recorded on the eCRF including all prescription, over-the-counter (OTC), herbal supplements, and IV medications and fluids. If changes occur during the study period, documentation of drug dosage, frequency, route, and date may also be included on the eCRF.

All concomitant medications received within 28 days before the first dose of investigational product and 30 days after the last dose of investigational product should be recorded.

Confidential

Document State: Effective (Controlled)  
CONFIDENTIAL

Page 65 of 118

Concomitant medications administered after 30 days after the last dose of investigational product should be recorded for SAEs and AESIs as defined in Section 8.4. In addition, all prior therapies for ACC should be recorded.

Allowed concomitant therapies:

- Glucocorticoids may be administered for treatment of infusion reaction and as premedication to prevent further infusion reaction (maximum daily dose of prednisone or equivalent  $\leq$  10 mg/day).
- In Cohort 2, in case of toxicity (e.g., GI AEs), per discretion of the Investigator and in consultation with the Sponsor's Medical Monitor, dexamethasone (Refer to Section 7.1.2) will be permitted.
- Palliative radiation therapy to a limited field (e.g., painful bone metastasis, painful lumps), *if it is not the sole site of measurable and/or assessable disease*, is allowed any time during study participation with prior approval of the Sponsor's medical monitor.
- Patients with castration resistant prostate cancer who have not undergone surgical orchiectomy can continue on medical therapies (i.e., gonadotropin releasing hormone [GnRH] analogs) to maintain castrate levels of serum testosterone. Concurrent treatment with ketoconazole or anti-androgens is not permitted, and patients who have discontinued these medications must have a washout period of at least 4 weeks or 5 half-lives of the drug (whichever is longer) prior to the first dose of investigational product.

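### Protocol Table 6, Section 6.6.2 and Section 7.1.3 give different instructions on dexamethasone for Grade 3–4 diarrhea, and nothing says which governs

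*Protocol*

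**What the plan says.** Four places in the protocol deal with the steroid.

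- **Table 6 (Section 6.6).** The Grade 3 and Grade 4 rows carry the same instruction in both cohort columns: "Treat with dexamethasone at a dose of 8 mg Q8h for up to 5 days". If symptoms have not improved, "the patient may continue with the dexamethasone or consider switching to budesonide 9 mg QD". The Grade 2 row gives the same dose permissively: "Patient may be treated with dexamethasone at a dose of 8 mg Q8h for up to 5 days".
- **Section 6.6.2, item 4.** The trigger is "For Grade 2 or higher diarrhea that is not adequately controlled with loperamide and dose interruption", and then "administration of dexamethasone may be considered at the discretion of the treating physician/investigator". The item reports that "administration of dexamethasone 8 mg to 10 mg daily, followed by tapering over several days, may have contributed to the improvement of diarrhea". It later suggests the same daily amount, with a taper, for co-administration with future AL101 doses.
- **Section 7.1.3 (allowed medications).** One bullet permits dexamethasone "In Cohort 2, in case of toxicity (e.g., GI AEs), per discretion of the Investigator" and in consultation with the Medical Monitor, referring to Section 7.1.2 for detail. The section opens with a general allowance for any treatment the Investigator judges necessary.
- **Section 7.1.2.** This is a corticosteroid premedication schedule for all patients. It contains no regimen for treating established diarrhea.

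For diarrhea management, Table 6 sends Grade 2 patients in both cohorts, and Grade 3 patients in Cohort 2, to Section 7.1.2. Only the Grade 3 cell for Cohort 1 points to Section 6.6.2.

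**The concern.** A site treating Grade 3 diarrhea finds a direction in one place, a discretionary option with an extra precondition in a second, and in a third a permission that names one cohort and adds a consultation step. None of these places says that another takes precedence.

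The stakes are patient safety first, then interpretation. Table 6 ends AL101 for Grade 2 or 3 diarrhea that has not returned to Grade 1 by 14 days, so how an episode is treated may bear on who stays on drug. At Grade 4 AL101 stops regardless, so there the disagreement concerns only steroid management. Diarrhea and discontinuation rates are tabulated by cohort (SAP 7.1.1, 7.3.1 and 7.8.2), and a reader of those tables would want to know what management lay behind them.

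The protocol also relies on its toxicity guidelines. Section 1.4.1 cites them in support of the 6 mg cohort and credits them with the low Grade 3 diarrhea rate seen so far. Instructions that carry that weight should read one way.

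**Working it through.** No statistical figure is involved, so the check sets the passages side by side and then does the dose arithmetic.

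| Point | Table 6 | Section 6.6.2 item 4 | Section 7.1.3 |
|---|---|---|---|
| Given or optional, Grade 2 | optional | optional | Investigator discretion; no grade stated |
| Given or optional, Grades 3–4 | directed | optional | Investigator discretion; no grade stated |
| What must fail first | Grade 3: antidiarrheals failed or Grade 3 reached; dose interruption not required | loperamide and dose interruption | not stated |
| Cohorts | both | no limit | Cohort 2 named |
| Medical Monitor consultation on the steroid | not required | only for co-administration with later AL101 doses | required |
| Dose for the current episode | 8 mg every 8 hours | none ordered | none; refers to 7.1.2 |
| Duration | up to 5 days, then may continue, no end stated | none | none |
| Taper | not stated | mentioned with the 8–10 mg | none of its own |

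**Where they conflict.** At Grades 3–4, directed and optional cannot both hold, because item 4 covers everything from Grade 2 upward. The prerequisite (failed dose interruption), the cohort named and the consultation step also differ. At Grade 2, Table 6 and item 4 are both permissive, so there is no conflict there on whether dexamethasone is given.

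**Dose under Table 6.** 8 mg × (24 h / 8 h) = 24 mg a day; 24 × 5 = 120 mg over 5 days.

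**Dose mentioned in 6.6.2.** 8–10 mg daily. The ratios are 24/10 = 2.4 and 24/8 = 3.0, but they do not compare two orders for the same use. Item 4 reports the lower figure as experience in a few cases and then suggests it around future infusions.

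**Where the cross-references lead.** The four cells (Grades 2 and 3, two cohorts) split 3 to Section 7.1.2 and 1 to Section 6.6.2. Section 7.1.2 describes 8 + 8 + (4 × 8) = 48 mg around each infusion, or 8 + 8 + (2 × 8) = 32 mg when reduced. That is prophylaxis tied to dosing, not management of an episode during which AL101 is interrupted.

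**How many patients.** In the earlier study, related diarrhea of Grade 3 or higher occurred in 8/43 = 18.6% at 4 mg weekly (Section 1.4.1). In this study Grade 3 diarrhea is given as 3.4% (Sections 1.3.2 and 1.4.1). If the denominator is the 29-patient safety set reported alongside it, that is 1/29. The two definitions are not identical. The 3.4% predates Cohort 2, and the documents give no rate at 6 mg in this study.

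**The case against.** The best defense is that only Table 6 is an order. Section 6.6.2 calls itself guidance that does not replace clinical judgment or an institutional protocol, Section 7.1.3 is a list of permitted medications, and Table 6 invites questions to the Medical Monitor. Some variation is therefore intended. The faulty cross-references each also point to the instructions in the same cell, so a site is not left without direction.

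Part of this stands: the cross-references are editorial errors with limited practical effect, and judgment is meant to play a role. It does not remove the conflict. Table 6's diarrhea text is itself labeled as guidelines, so the label does not rank one above the other, and direction and discretion at the same grade still need reconciling.

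Four stronger readings are tempting, and the documents do not support them.

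- *Two rescue doses that differ 2.4- to 3-fold.* Only Table 6 orders a dose for the episode. The 8–10 mg in 6.6.2 is reported experience and a suggestion for later infusions.
- *Cohort 1 is barred from dexamethasone.* Section 7.1.3 does not name Cohort 1, but its opening sentence allows any treatment judged necessary. Not named is different from prohibited.
- *Table 6 contradicts its own 5-day limit.* It reads as a reassessment at 5 days followed by options. The gap is that continuation has no stated end.
- *The comparison of 4 mg with 6 mg is biased.* The study is non-comparative, and SAP 7.5.2 treats each cohort as an independent trial. Rates are reported by cohort, not formally compared.

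**Conclusion.** The point holds in limited form. For Grade 3–4 diarrhea the protocol directs dexamethasone in one place and leaves it to discretion, with a further precondition, in another. A third place names one cohort and adds a consultation step. Three of four cross-references lead to a premedication section, and no precedence is stated.

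That patients were in fact managed differently is an inference: the text allows it but does not show it. Any effect on staying on AL101 through the 14-day rule cannot be quantified from the documents, and for the given-or-optional conflict it can arise only at Grade 3. The number affected may be small at 4 mg if the 3.4% rate persists, and is unknown at 6 mg. The point has no bearing on sample size, power or type I error. It merits correction because it concerns safety instructions and is cheap to resolve. Which instruction is clinically right is not judged here.

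**What to change.** Reconcile Table 6, Section 6.6.2 item 4 and Section 7.1.3 into one statement covering:

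- whether dexamethasone is given or optional at each grade, and what must be tried first;
- which cohorts are covered, and whether Medical Monitor consultation is needed;
- dose, duration (including any continuation) and taper.

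Alternatively, state which section prevails. Correct the Table 6 cross-references so that both cohorts are sent to the same diarrhea section. The sponsor's clinical team decides the content.

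The cost is amendment wording, with no added procedures or patients. The SAP was updated shortly before database lock and carries a July 31, 2022 censoring date, so an amendment may come too late to alter much conduct. In that case the study report should say which instruction sites were told to follow.
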